5.4 Follow-up Procedures

Subjects will be followed every month after completion of (or early withdrawal from) study treatment until testing returns to baseline. Toxicity monitoring will be repeated (including hematology, serum chemistries, QUIGs, sIgE) at 3 months after cessation of ibrutinib; if at this time they are not yet back to baseline, they will be repeated at 6 months.

- Physical exam, vital signs
- Urine Pregnancy test (if required)
- CBC
- CMP

- Immunoglobulin levels
- Skin prick testing

5.5 Time and Events Table

5.4.1. Part 1

Visit	1	2	3 ^a	4/Early Termination	End-of-Study
	Screening / Day 0	Day 2	Day 4 or Day 7	Every 7 days until all allergy testing returns to baseline positive	Final Visit when all allergy testing is positive
Informed Consent	X				
Skin prick testing	X	X	X	X	
Basophil activation test	X	X	X	X	
History and PE	X				X
Toxicity (include DLT) Evaluations	X	X	X	X	X
CBC	X	X	X	X	X
CMP	X	X	X	X	X
EKG	X				X
Urine pregnancy testing ^b	X	X	X	X	X

^a If required

^b Females of child-bearing potential only

5.4.2. Part 2

Visit	1	2	3
	Screeing / Day 0	Day 2	Follow up (3 and/or 6 months after Visit 2)
Informed Consent	X		
Skin prick testing	X	X	X
Basophil activation test	X	X	
SBPC food challenge	X	X	
History and PE	X	X	X

Toxicity (include DLT) Evaluations	X	X	X
CBC	X	X	X
CMP	X	X	X
EKG	X	X	
Urine pregnancy test ^b	X		

^b Females of child-bearing potential only

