for toxicities (see below). After this visit, subjects will be given ibrutinib (two doses of 420 mg of ibrutinib to start the following day and to be taken orally at 8am exactly 24 hours apart) and return for **Visit 2** to undergo repeat PST and phlebotomy for testing preformed in an identical manner to Visit 1. If two consecutive doses of 420 mg of ibrutinib given 24 hours apart is insufficient to cause >80% inhibition of the SPT and BAT response, subjects will be given two additional doses of 420 mg of ibrutinib to continue to take at 8am exactly 24 hours apart for two more days, and return for **Visit 3** for identical repeat testing as in Visits 1 and 2. If four consecutive doses of 420 mg of ibrutinib given 24 hours apart is insufficient to cause >80% inhibition of the SPT and BAT response, subjects will be given three additional doses of 420 mg of ibrutinib to continue to take 24 hours apart for three more days, and return for **Visit 4** for identical repeat testing as in Visits 1, 2 and 3, where based on preliminary data, we expect SPT and BAT to be suppressed. Once both the SPT and BAT responses are inhibited, no further ibrutinib doses will be given, and subjects will return on a weekly basis until both the peanut/tree nut PST and BAT return to at least 80% of baseline values. At this point, Part 1 will have been completed. At each visit, patients will be monitored for toxicities, including CBC, CMP, and pregnancy testing. Prior to drug initiation and at the end of the trial, an EKG will be performed.

Clinical protocol for part 1 (top) and part 2 (bottom). * or - = predicted response; ??? = question to be answered; * = if needed

and subjects will return on a weekly basis until both the peanut/tree nut PST and BAT return to at least 80% of baseline values. At this point, Part 1 will have been completed. At each visit, patients will be monitored for toxicities, including CBC, CMP, and pregnancy testing. Prior to drug initiation and at the end of the trial, an EKG will be performed.

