4.0 TREATMENT PLAN

4.1 Treatment Dosage and Administration

For Part 1 of the study, we will determine the length of treatment (i.e., the number of daily doses) required to inhibit both basophil and food skin test responses. Preliminary data demonstrates that 7 days of treatment will inhibit both basophil and mast cell responsiveness to aeroallergens, but have not yet tested shorter time points. Prior studies in cancer subjects suggest that one dose is sufficient to completely inhibit BAT, but we propose a minimum of two doses to allow for diffusion and penetration of ibrutinib into the skin compartment where our SPT is performed to assess skin mast cell responsiveness. For Part 1, 6 subjects will take ibrutinib 420 mg, by mouth once daily (every 24 hours) on an outpatient basis. After two days, the subject will undergo blood testing and SPT to assess basophil and mast cell reactivity. If both tests are negative, Part 1 is completed. If both tests are not negative, then the subject will take 2 more days of ibrutinib (same dose, for a total of 4 doses), and identical testing will be repeated. If testing is not negative at day 4, the subject will take 3 more days of ibrutinib (same dose, for a total of 7 doses), which is the maximum anticipated number of doses needed to suppress both the BAT and SPT.

For Part 2 of the study, 6 subjects will take ibrutinib 560 mg once daily by mouth (every 24 hours) for 2 days, which is the minimum number of days required to cause $\geq 80\%$ inhibition of food SPT and BAT responses as determined in part 1. Part 2 will last a minimum of 3 days.

Dose-limiting toxicity (DLT) includes any grade 3 or 4 hematologic toxicity, grade 3 hepatotoxicity or increase in creatinine $\times 2.5$ normal limit. DLT will be monitored at each visit, at any time during treatment.

Maximally tolerated dose (MTD) will occur at the point DLT occurs. Ibrutinib is approved as a daily medication for another indication, and we propose to use the drug in adults only at its approved oral dosing of 420 or 560 mg daily for a minimum of two days and a maximum of 7 days. Dose limiting events include grade 3 or 4 hematologic events, grade 3 or 4 hepatotoxicity, AST or ALT >3 times normal range, creatinine >2.5 times normal range. DLT evaluation will be completed throughout the study, anytime during treatment.

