4.5 Duration of Follow Up

Subjects will be followed until SPT and BAT return to baseline in Part 1, and for up to 6 months after cessation of ibrutinib treatment in Part 2. Subjects removed from treatment for unacceptable adverse events will be followed until resolution or stabilization of the adverse event.

Subjects will be removed from therapy when any of the criteria listed in Section 5.5 apply. The Principal Investigator will be notified. The reason for study removal and the date the subject was removed will be documented in the Case Report Form. The subject will be followed-up per protocol.

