5.1.13 Spirometry

To be performed before SBFC if the patient has a history of asthma or exercise-induced bronchospasm.

5.2 Procedures During Treatment (Part 1)**5.2.1 Screening visit (Day 0) (Screening visit testing will be completed before drug administration)****Screening:**

- Physical exam, vital signs
- CBC
- CMP
- Immunoglobulin levels
- EKG
- Urine Pregnancy test (if required)

Procedures (to be done only if labs and EKG are within normal limits):

- Skin-prick testing
- Basophil activation test

5.2.2 Day 2 (or 4 or 7 depending on when skin testing and basophil activation test return to baseline)

- Skin prick testing
- Basophil activation test
- Hematology
- Serum chemistries
- Immunoglobulin levels

5.2.3 After treatment termination (Termination and End of Study visits; time point determined when both skin prick testing and basophil activation testing return to baseline)

- Physical exam, vital signs
- Hematology
- Serum chemistries
- Immunoglobulin levels
- EKG
- Urine Pregnancy test (if required)

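### Part 1 length of effect after stopping ibrutinib (objective 2.2.3): the protocol gives inconsistent rules for when recovery testing ends

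*Combined protocol and SAP*

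**What the plan says.** Objective 2.2.3 concerns a duration: how long SPT and BAT stay inhibited after the last dose. Its endpoint in section 2.3 is a change in SPT size and in percent basophil activation. It gives neither a time nor a recovery threshold. Section 10 defines only the 80% reduction that marks inhibition.

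The event that ends Part 1 recovery testing is worded in three ways:

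- **Study Schema, Part 1:** "subjects will return on a weekly basis until both the peanut/tree nut PST and BAT return to at least 80% of baseline values". Part 1 is then complete. (I read PST here as the skin prick test.)
- **Sections 4.5 and 5.2.3:** "Subjects will be followed until SPT and BAT return to baseline in Part 1", and "time point determined when both skin prick testing and basophil activation testing return to baseline". Neither gives a margin.
- **Section 5.5, table 5.4.1:** the weekly column reads "Every 7 days until all allergy testing returns to baseline positive" and the End-of-Study column reads "Final Visit when all allergy testing is positive". No cut-off for a positive test appears here or in inclusion criterion 3.1.3.

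Three other places bear on the point:

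- Section 5.4 names no part of the study. It sets monthly follow-up until testing is back at baseline, and its list includes SPT but not BAT.
- Section 4.1, on dosing, says "If both tests are negative, Part 1 is completed", which is the point of suppression.
- Section 5.2.2 sets the on-drug test day "depending on when skin testing and basophil activation test return to baseline", using for suppression the phrase that 5.2.3 uses for recovery.

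**The concern.** The recovery event does two jobs: it is the time that objective 2.2.3 needs, and it ends testing. The three wordings are not equivalent. The schema treats a test as not yet suppressed when dosing is "insufficient to cause >80% inhibition of the SPT and BAT response", so suppression means below 20% of baseline. Between 20% and 80% of baseline, a test can be positive without having recovered under the schema rule.

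If a subject's weekly testing is closed in that band, the time to 80% is never observed. The visit-by-visit comparison with baseline in section 10.3 cannot restore it, and table 5.4.1 schedules no SPT or BAT at the End-of-Study visit. With 6 Part 1 subjects and descriptive reporting, one or two such closures would change the reported duration.

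**Working it through.** The plan gives no figure for this endpoint, so there is none to reproduce. The check compares the rules and then illustrates how far apart they can be.

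**Inputs from the protocol:** weekly visits (schema and table 5.4.1); suppression below 20% of baseline and recovery at 80% or more (schema); 6 subjects in Part 1 (section 4.1); study duration 12 weeks (Study Summary).

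**Assumptions, none of them in the protocol:** both tests recover linearly from 0 to 100% of baseline by day R; a positive test means at least 20% or at least 50% of baseline; measurement CV is 10%, 20% or 30%.

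**1. Without measurement error.** With cut-off c as a share of baseline, the recorded day is 7 × ceil(c × R / 7). For R = 28: c = 0.5 gives 7 × ceil(14/7) = 14, and c = 0.8 gives 7 × ceil(22.4/7) = 28.

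| Full recovery (R) | Positive at 20% | Positive at 50% | At least 80% | Full baseline |
|---|---|---|---|---|
| day 7 | 7 | 7 | 7 | 7 |
| day 14 | 7 | 7 | 14 | 14 |
| day 28 | 7 | 14 | 28 | 28 |
| day 42 | 14 | 21 | 35 | 42 |
| day 56 | 14 | 28 | 49 | 56 |

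On these values, an any-positive rule closes testing 0, 7, 21, 21 or 35 days before the 80% event at the 20% cut-off, and 0, 7, 14, 14 or 21 days before it at the 50% cut-off. The any-positive and 80% rules agree up to R = 8.75 days, because 0.8 × 8.75 = 7. The 80% and full-baseline rules differ by 0 to 7 days in the table.

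**2. With measurement error.** I simulated 200,000 subjects per scenario, with independent lognormal error on each reading, one baseline reading with the same error, and weekly visits to day 84. The result is the share whose testing stops before the first visit with both tests at 80% or more:

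- Cut-offs 20% and 50%, CV 10–30%, R = 14 to 42: 35% to 100%. At CV 20% and R = 28 the shares are 100% and 87%.
- Cut-off 70%, same grid: about 10% to 55%.
- R = 7, CV 10%: about 11%. These subjects have fully recovered and miss the 80% mark through noise alone.

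**3. The no-margin rule.** In a fully recovered subject, the chance that both tests pass at one visit under the 80% rule is Φ(−ln 0.8 / (s√2))², with s² = ln(1 + CV²). This gives 0.890, 0.620 and 0.496 at CV 10%, 20% and 30%. With no margin it is 0.5 × 0.5 = 0.25 at any CV. The median number of extra weekly visits is 3, 2 and 1 at those CVs. With R = 14 to 42, between 26% and 34% of subjects have still not met the no-margin rule by day 84, which is the stated 12 weeks. Their 80% time can still be read from the recorded values.

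**The case against.** The strongest reply is that the schema holds the only numeric recovery rule and the other wordings are shorthand for it. The table supports this in part. The bare word positive heads a close-out column with no SPT or BAT scheduled. Testing is governed by the weekly column, whose wording includes a return to baseline. On that reading nothing is lost; at most some subjects attend extra visits. This reply stands as a plausible reading. However, no text makes the link, and none ranks the schema above the table that staff use to schedule visits.

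The size is also open to challenge, and that challenge stands. The day counts and percentages follow from the chosen cut-offs and recovery speeds. Fast recovery makes the gap vanish in the error-free case, and a cut-off near 80% makes it small.

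A reader might draw two stronger conclusions, and the documents support neither:

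- **That Part 1 ends at suppression, so no recovery data are collected.** The sentence in 4.1 sits in the dosing section. The schema, 4.5, 5.2.3 and table 5.4.1 all require testing afterwards. Likewise, 5.2.2 is tied to the Day 2, 4 or 7 visits and is unlikely to be taken for a recovery rule. Both are minor slips.
- **That 5.4 is a Part 2 section and should be limited to it.** Its heading and text name no part, and it covers everyone who completes or leaves treatment. Limiting it could remove the 3- and 6-month toxicity checks from Part 1 subjects.

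**Conclusion.** The concern holds as an inconsistency between stated rules. The duration reported for 2.2.3 depends on whether staff follow the 80% rule, a no-margin return to baseline, or a positive result. Only the last, read as any positive test, loses information, and then the time to 80% of baseline is not recoverable. The no-margin reading costs visits, not data.

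No single size can be given. The illustrated loss runs from 0 to 35 days without measurement error, and is zero if recovery is complete within about a week. It rests on linear recovery, the weekly schedule and assumed cut-offs of 20% and 50%. A reader might infer that most subjects will be closed early. The documents do not support that, because they give no recovery speed, cut-off or measurement error, and the weekly column does refer to baseline.

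The monthly interval in 5.4 conflicts with weekly Part 1 testing. It also conflicts with Part 2 follow-up starting at 3 months (Study Schema, table 5.4.2), which is a separate matter. The objective is secondary and descriptive in 6 subjects, so no primary endpoint, alpha or power is affected. Low priority.

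**What to change.** 1. In 2.3, define the 2.2.3 endpoint as the time from last dose to the first weekly visit at which SPT and BAT are each at least 80% of the subject's own baseline. Report any subject closed before that as not having reached it.
2. Use that event in 4.5, 5.2.3 and the two post-treatment columns of table 5.4.1, in place of the baseline and positive wordings.
3. In 5.4, state that Part 1 allergy retesting (SPT and BAT) is weekly, as in the Study Schema. Leave the 3- and 6-month toxicity follow-up unchanged for all subjects. Whether Part 2 follow-up is monthly or starts at 3 months is for the sponsor to settle separately.
4. At the same time, 4.1 can say that suppression ends dosing rather than Part 1, and 5.2.2 can say that the tests are inhibited.

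The cost is wording only. The weekly visits and the 80% rule are already in the schema, so no visits, tests or subjects are added. Sections 1.2 and 4.1 indicate that Part 1 results already exist. For subjects already followed, the endpoint in item 1 can be applied to their recorded values.

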Part 2: Visit 1 will be identical to those for Part 1 except that subjects will take a higher dose of ibrutinib (560mg daily) for 2 days and a single-blind, placebo-controlled (SBPC) graded food challenge of up to 8 mg of peanut or tree nut protein, administered over escalating doses, will be performed in a monitored at the study site in a clinical research unit (CRU) setting. Prior to the SBPC food challenge, 30 mL of peripheral blood will be collected for BAT, sIgE to peanut and components, as well as for total IgE, eosinophil and basophil enumeration. During the challenge, subjects will be repeatedly assessed for signs and symptoms of food-induced anaphylaxis between each dose per food challenge protocol. This visit will establish each subject's baseline threshold dose for peanut/tree nut reactivity.

Once a confirmed reaction occurs, the food challenge will be terminated and the reaction treated until it has resolved. Within 15 minutes of a positive challenge, an additional 10 mL of blood will be drawn for mast cell microparticle analysis. After a minimum of a two week recovery period, each subject will then begin taking ibrutinib 560 mg orally daily for 2 days, which is the minimum number of doses that

demonstrate efficacy as determined in Part 1. Two hours after the final dose, subjects will return to the study site for **Visit 2**, and PST and SBPC food challenges will be repeated to establish each subject's new threshold dose for peanut/tree nut reactivity while on ibrutinib, and with repeat post-challenge blood collection for mast cell microparticle analysis. At this point of the protocol, ibrutinib dosing will be stopped. Follow up visits starting 3 months after cessation of ibrutinib will be conducted to repeat toxicity labs and skin testing.

STUDY SUMMARY

Title	Inhibition of Anaphylaxis by Ibrutinib
Protocol Number	BB20150924
Phase	Phase 2
Methodology	Open label study to determine dosing and safety of Ibrutinib for the treatment of food allergy
Study Duration	12 weeks
Study Center(s)	Single-center

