3.1 Inclusion Criteria

- 3.1.1 History of food allergy to peanut (or tree nut).
- 3.1.2 Male or female age \geq 18 years.
- 3.1.3 Positive skin prick testing and basophil activation test to the trigger food(s), either peanut and/or tree nut(s).
- 3.1.4 Clinical reaction to oral food challenge at baseline (for Part 2 only)
- 3.1.5 Adequate organ and marrow function as defined below:

- leukocytes	\geq 3,000/mcL
- absolute neutrophil count	\geq 1,500/mcL
- platelets	\geq 100,000/mcL
- total bilirubin	within normal institutional limits
- AST(SGOT)/ALT(SPGT)	within normal institutional limits
- Creatinine	within normal institutional limits
- 3.1.6 Women of child bearing potential must agree to two forms of highly effective contraception (hormonal, device, or barrier method of birth control; abstinence) prior to study entry, for the duration of study participation, and for 90 days following completion of therapy. Should a woman become pregnant or suspect she is pregnant while participating in this study, she should inform the Principal Investigator and her treating physician immediately.
 - 3.1.5.1 A female of child bearing potential is any woman (regardless of sexual orientation, having undergone a tubal ligation, or remaining celibate by choice) who meets the following criteria:
 - Has not undergone a hysterectomy or bilateral oophorectomy; or
 - Has not been naturally postmenopausal for at least 12 consecutive months (i.e., has had menses at any time in the preceding 12 consecutive months).
- 3.1.7 Ability to understand and the willingness to sign a written informed consent.
- 3.1.8 Ability to clearly understand and speak English at an 8th grade reading level. For safety reasons, subjects must speak English due to the anticipated need for clear and timely communication with investigators and the study team in emergency situations, since the investigators and study team are English speaking.

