3.2 Exclusion Criteria

- 3.2.1 Subjects who have been on immunomodulatory therapies or oral corticosteroids within 1 month prior to study participation will be excluded, and those taking antihistamines must stop these drugs for one week prior to enrollment and must refrain from taking antihistamines during the duration of the study so as not to interfere with SPT responses.
- 3.2.2 Subjects with symptoms not consistent with type 1 food reactions (atopic dermatitis, eosinophilic esophagitis and any other non-IgE-mediated food sensitivities) will be excluded.

- 3.2.3 History of allergic reactions attributed to compounds of similar chemical or biologic composition to ibrutinib.
- 3.2.4 Uncontrolled inter-current illness including, but not limited to, ongoing or active infection, symptomatic congestive heart failure, unstable angina pectoris, cardiac arrhythmia, beta-blocker use or psychiatric illness/social situations that would limit compliance with study requirements.
- 3.2.5 Subjects must not be pregnant or nursing due to the potential for congenital abnormalities and the potential of this regimen to harm nursing infants.
- 3.2.6 Subjects on anticoagulants, anti-platelet therapy, or any other predisposition towards bleeding.
- 3.2.7 Subjects with history of idiopathic urticaria, dermatographism, idiopathic or unexplained anaphylaxis, or anaphylaxis (to foods or otherwise) resulting in intubation, prolonged hypotension, or neurological sequelae

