5.0 STUDY PROCEDURES**5.1 Screening/Baseline Procedures**

Assessments performed exclusively to determine eligibility for this study will be done only after obtaining written informed consent. Assessments performed for clinical indications (not exclusively to determine study eligibility) may be used for baseline values even if the studies were done before informed consent was obtained.

All screening procedures must be performed within 14 days prior to start of treatment. The screening procedures include:

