5.1.11 Pregnancy test (for females of child bearing potential)

See section 3.1.6.1 for definition.

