5.3 Procedures During Treatment (Part 2)

5.3.1 Screening/Baseline visit (Visit 1)

Screening:

- Physical exam, vital signs
- Urine Pregnancy test (if required)
- CBC
- CMP
- Immunoglobulin levels
- EKG
- Spirometry (only if the subject has a history of asthma)

Procedures (to be done only if labs and EKG are within normal limits)

- Skin prick testing
- Basophil activation test
- SBPC oral food challenge as follows:

All oral food challenges (OFC) shall be performed as single (patient)-blinded, placebo controlled food challenges according to standard published guidelines (11, 12). Placebo challenge and active challenge will be performed in that order on the same day if the subject has no symptoms during the first (placebo) challenge. If a reaction requiring treatment occurs during the first challenge, the next challenge should not be performed until the symptoms have subsided. Oral food challenge to peanut or tree nut protein will be performed according to standard operating procedure. At physician discretion, based upon history and possible subjective or very mild objective symptoms during a challenge, dosing intervals may be extended.

Actions to minimize risk of severe allergic reactions during oral food challenge (OFC):
Prior to the OFC visit, subjects will be told to contact study staff about asthma and seasonal allergy symptoms, fever, acute infections including upper respiratory infections, rashes or change in status of chronic medical conditions. OFCs will be rescheduled in the event that any of these occur. Study staff will contact subjects 1-3 days before the OFC to inquire about recent symptoms.

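### Part 2 schedules no pregnancy test between Visit 1 and the first 560 mg dose, which comes at least 14 days later

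*Combined protocol and SAP*

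**What the plan says.** **Timing of the test.** Section 5.3.1 lists a urine pregnancy test among the Part 2 Visit 1 screening items. In table 5.4.2 (within section 5.5) the row "Urine pregnancy test ^b" has a mark under Visit 1 and blanks under Visits 2 and 3. The Visit 2 list in 5.3.2 has no pregnancy test.

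**Timing of dosing.** The Study Schema places the baseline food challenge at Visit 1 and continues: "After a minimum of a two week recovery period, each subject will then begin taking ibrutinib 560 mg orally daily for 2 days". No maximum recovery time is given. On Visit 2 it says: "Two hours after the final dose, subjects will return to the study site for" that visit. No Part 2 visit is defined between Visit 1 and the first dose.

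**The screening limit.** Section 5.1 states: "All screening procedures must be performed within 14 days prior to start of treatment". The pregnancy test is one of those procedures (5.1.11). Section 5.1 is not confined to Part 1, because 5.1.13 ties spirometry to the food challenge, which only Part 2 has.

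**Why pregnancy matters here.** Exclusion 3.2.5 reads: "Subjects must not be pregnant or nursing due to the potential for congenital abnormalities". Section 1.2 puts ibrutinib in pregnancy category D, and 7.1.2.5 warns of fetal harm. On prevention, 3.1.6 says: "Women of child bearing potential must agree to two forms of highly effective contraception". It also asks a woman who suspects pregnancy to report it at once.

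**The concern.** On the schedule as written, a woman who conceives during recovery, or whose pregnancy was too early to show at Visit 1, could take both 560 mg doses without a further test. Pregnancy is an exclusion, yet no scheduled check confirms its absence when the drug is taken. The removal and reporting provision (item 5.5.6 in section 5.6) acts only once a pregnancy is known.

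The contrast with Part 1 is notable. Its table marks the test at every visit. Part 2 uses the higher dose and has a recovery period between test and dosing, but schedules no test in that interval. What is at stake is participant and fetal safety. No endpoint, analysis or error rate is involved.

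**Working it through.** The plan gives no figure to reproduce here. The check compares dates.

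**Notation.** Day 0 is the Visit 1 challenge. Let *s* ≥ 0 be the days from the screening test to the challenge, and *d* the day of the first 560 mg dose.

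**Inputs**
- Recovery rule (Study Schema, Part 2): *d* ≥ 14, no upper bound.
- Screening limit (5.1): test no more than 14 days before treatment starts.
- Visit 2 (Study Schema): two hours after the second daily dose, so on day *d* + 1.
- Scheduled Part 2 tests before dosing (5.3.1, table 5.4.2): one, at Visit 1.

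**Step 1: age of the last scheduled test at first dose.** Age = *d* + *s* ≥ 14 + 0 = 14 days.

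**Step 2: can the Visit 1 test satisfy 5.1?** The limit needs *d* + *s* ≤ 14, while recovery needs *d* ≥ 14. Only *d* = 14 with *s* = 0 meets both, so there is no slack. With *s* = 0 and illustrative dosing days:

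| First dose (day) | Age of test (days) | Beyond the 14-day limit (days) |
|---|---|---|
| 14 | 14 | 0 |
| 15 | 15 | 1 |
| 21 | 21 | 7 |
| 28 | 28 | 14 |

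If the screening test precedes the challenge by even one day, the limit is missed at the minimum recovery too. That is plausible, since 5.3.1 makes the challenge conditional on normal laboratory and EKG results.

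**Step 3: can a later visit supply the test?** Visit 2 falls on day *d* + 1 ≥ 15, after both doses. Neither its list nor its table cell includes the test. Follow-up testing (5.4) comes after treatment. Scheduled tests after recovery and before the first dose: 0.

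**Step 4: size of the unprotected window.** Let *L* be the days from conception to a positive urine test. The documents give no value; I assume 7 to 21. Take the most favourable case, *d* = 14 and *s* = 0. Conceptions missed before the first dose span 14 + *L* days as scheduled, and *L* days with a test on the first dosing day. The share removed is 14/(14 + *L*).

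| *L* (assumed) | As scheduled | Test on first dosing day | Share removed |
|---|---|---|---|
| 7 | 21 days | 7 days | 14/21 = 67% |
| 14 | 28 days | 14 days | 14/28 = 50% |
| 21 | 35 days | 21 days | 14/35 = 40% |

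The scheduled window grows by one day for each further day of recovery. The window with a dosing-day test does not.

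**The case against.** The best counter-argument is that the control already exists. The limit in 5.1 runs back from the start of treatment, not from Visit 1, and 11.4 requires the study to be run exactly as written. For any first dose after day 14, dosing on the Visit 1 test alone would be a deviation. For a dose on day 14 with same-day screening, the protocol's own limit is met, and a fresher test is a tighter standard than the plan chose. This is right as far as it goes, and nothing bars a repeat test. But 5.1 never mentions repeating a test; the need has to be inferred. Staff working from the Part 2 lists and table would find no visit, list item or cell that prompts one.

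A second argument is that table 5.4.2 labels the visits Day 0 and Day 2, and 4.1 gives Part 2 a minimum of 3 days, which would put the test close to dosing. Those labels cannot count from the challenge, given the explicit two-week recovery. They make the gap harder to see.

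Third, the Study Schema calls for pregnancy testing at each visit in Part 1, and Part 2 Visit 1 is modelled on Part 1. Even if that carries over, there is no visit between Visit 1 and dosing for it to apply to.

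Three points stand. The risk is already reduced by two-form contraception and the duty to report a suspected pregnancy. Section 7.1.2.5 places the rat malformations at 14 times the exposure at 560 mg per day, although reduced fetal weights occurred at lower exposures. And the 14-day limit applies equally to the other screening procedures, such as CBC, CMP and EKG, so a urine test alone does not settle 5.1 for those. That widens the issue and does not answer it.

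**Conclusion.** The concern holds and should be fixed. At the first 560 mg dose the last scheduled pregnancy test is at least 14 days old, and no test is scheduled after recovery and before dosing. The Visit 1 test meets 5.1 only in one exact case: screening on the challenge day and dosing on day 14. These results use only the protocol's own rules.

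The 40% to 67% reduction rests on the assumed 7 to 21 days to a positive test and on dosing on day 14. It is a share of a time window, not a probability of exposure, and takes no account of contraception. A pre-dose test would still miss a very recent conception. The gap affects women of child-bearing potential among the 6 Part 2 subjects, for two doses.

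**What to change.** Require a negative urine pregnancy test in women of child-bearing potential after recovery and before the first 560 mg dose, for example when the drug is dispensed. Add it to 5.3 and to table 5.4.2 as a pre-dose column or footnote, and state that it is the repeat needed under the 14-day limit in 5.1. A test added at Visit 2 would not do, because both doses have been taken by then. The same footnote could say whether the other 5.1 procedures must also be renewed when recovery runs past the limit.

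Two editorial corrections belong with this: mark the Visit 3 cell to agree with the follow-up list in 5.4, and say what Day 2 and the 3-day minimum are counted from.

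The cost is one urine test per affected subject among 6 and short text edits. A brief pre-dose contact may also be needed if the drug is handed out at Visit 1; section 9.2 does not say when Part 2 drug is dispensed.
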